3.4.4 Laboratory data

Laboratory data will be collected throughout the study, from screening to 30-day follow-up visit as described in [Appendix C](#). Blood and urine samples for determination of pregnancy, haematology, clinical chemistry, and urinalysis will be collected as described in Section 5.2.1 of the CSP. For derivation of post baseline visit values considering visit window and how to handle multiple records, derivation rules as described in Section 3.4.9 below will be used.

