- To prevent very large tables or plots being produced that contain many cells with meaningless data, for each treatment group visit data should only be summarised if the number of observations is greater than the minimum of 20 and $> 1/3$ of patients dosed. For example, if 150 patients were dosed in the study ($1/3 * 150 = 50$), data at a particular visit would be summarised if the number of observations is greater than min (20, 50). This would be in each treatment group. Eg, if olaparib arm at Visit 6 has > 20 observations and placebo arm has < 20 observations, the visit data will be summarised for the olaparib arm but not the placebo arm. If both had < 20 patients, the data for that visit will be presented as ‘NC’ (Not Calculated). (This does not apply to PRO data.)
- For summaries at a patient level, all values should be included, regardless of whether they appear in a corresponding visit based summary, when deriving a patient level statistic such as a maximum.
- Baseline will be defined as the last non-missing measurement prior to dosing with study treatment (olaparib or placebo). Any assessments made on day 1 will be considered pre-dose. If an assessment on day 1 is identified as baseline, then it will not be considered as “on treatment”. Where safety data are summarised over time, study day will be calculated in relation to date of first treatment (olaparib or placebo).

Imputation of missing safety data

Missing safety data will generally not be imputed. However, safety assessment values of the form of “ $< x$ ” (ie, below the lower limit of quantification) or “ $> x$ ” (ie, above the upper limit of quantification) will be imputed as “ x ” in the calculation of summary statistics but displayed as “ $< x$ ” or “ $> x$ ” in the listings.

Imputation of missing age

- Age at randomisation: Age at randomisation (baseline) will be calculated from the date of birth. Due to country specific regulations the full date of birth will not be available for all patients. In this case the “age as collected” from the demographics CRF will be used instead.

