4.2.13 Safety

Safety data will be summarised and listed only. No formal statistical analyses will be performed on the safety data. All safety data will be summarised by actual treatment group (olaparib or placebo). However, some listings such as AEs listings will display the actual dose the patient received at onset of an AE.

Adverse events

All AEs, both in terms of Medical Dictionary for Regulatory Activities (MedDRA) preferred term (PT) and Common Toxicity Criteria for Adverse Events (CTCAE) grade, will be listed and summarised descriptively by count (n) and percentage (%) for each treatment group. MedDRA dictionary will be used for coding. Any AE occurring before olaparib/placebo treatment (ie, before Study Day 1) will be included in the AE listings, but will not be included in the summary tables (unless otherwise stated). These will be referred to as 'pre-treatment'.

The summary tables will include all AEs that occurred after the start of treatment up until the end of the 30 day follow-up period. The 30 day follow-up period will be defined as 30 days following discontinuation of olaparib/placebo treatment. Any untoward event occurring subsequent to the 30-day follow-up AE reporting period that the investigator assesses as possibly related to the study treatment will also be included in the AE listings, but not in the summary tables.

All reported AEs will be listed along with the date of onset, date of resolution (if AE is resolved), investigator's assessment of severity and relationship to study drug. Frequencies

and percentages of patients reporting each PT will be presented (ie, multiple events per patient will not be accounted for apart from on the episode level summaries).

Summary information (the number and percent of patients by actual treatment) will be tabulated for:

- All AEs
- All AEs causally related to study medication
- AEs with CTCAE grade 3 or higher
- AEs with CTCAE grade 3 or higher, causally related to study medication
- AEs leading to dose modification of olaparib/placebo
- AEs leading to dose interruption of olaparib/placebo
- AEs leading to dose reduction of olaparib/placebo
- AEs with outcome of death
- AEs with outcome of death causally related to study medication
- All SAEs
- All SAEs causally related to study medication
- DAEs
- AEs leading to discontinuation of olaparib/placebo, causally related to study medication

An overall summary of the number and percentage of patients in each category will be presented.

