In addition, a truncated AE table of most common AEs, showing all events that occur in at least 5% of patients overall will be summarised by PT, by decreasing frequency. This cut-off may be modified after review of the data. Also, a truncated AE table of most common non-serious AEs, showing events that occur in at least 5% of patients on the PT level in at least one treatment group will be summarised by SOC and PT, by decreasing frequency.

Each AE event rate (per 1000 patient years) will be summarised by system organ class (SOC) and also by PT within each SOC. The event rate will be calculated as the number of patients with an AE in that SOC or with that PT divided by the sum of the duration of therapy (for

patients without such an event) and the time to the AE (for patients with such an event) in each group multiplied by 1000. The denominator defines the time at risk for an event with:

- Duration of therapy (days) calculated as:
MINIMUM([date of last dose + 30-day safety follow-up period], OS date, DCO) – date of first dose + 1
- Time to the AE (days) calculated as date of first occurrence of the AE – date of first dose + 1 (in days), imputed AE start dates can be used in case of missing start dates.

The formula for calculating the event rate for a specific PT is as follows:

CCI

CCI

CCI

AEs will be assigned CTCAE grades (National Cancer Institute CTCAE version 4.0) and summaries of the number and percentage of patients will be provided by maximum reported CTCAE grade, SOC, PT and actual treatment group. Tabulation will be repeated to present AEs with a CTCAE grade 3 or higher and separately those AEs, causally related to study treatment by SOC and PT. Fluctuations observed in CTCAE grades within the same PTs during study will be listed.

Tabulation of AEs causally related to study treatment will be summarised by SOC and PT and presented by treatment group.

Summaries of the number and percentage of patients with AEs leading to dose modification of olaparib/placebo and also separately with AEs leading to dose reductions and drug interruptions of olaparib/placebo will be presented by PT and treatment group.

A summary table will be prepared presenting AEs which started prior to first dose or > 30 days following date of last dose by SOC and PT. Data will be presented by treatment group.

Death

A summary of all AEs resulting in deaths will be provided with number and percentage of patients by actual treatment group, categorised as:

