Laboratory data is collected by local laboratories. Results will be converted to standard units for reporting purposes. Reference ranges from the local laboratories are collected in the CRF and will be used to determine reference range indicators (low, normal, high). If the same parameter is found as measured in serum and in plasma, then the summaries will not distinguish between them (e.g. values from plasma Albumin and serum Albumin will be summarised under Albumin). If the same parameter is found as measured in serum and in plasma within the same patient, which would be a rare case, then the change from baseline will only be calculated for those post-baseline values using the same source, i.e. only within plasma or serum. If one patient has multiple toxicity grades, because they are derived separately from serum and plasma, then the maximum value of the two will be considered.

For all continuous laboratory assessments, absolute value, change from baseline and percentage change from baseline will be summarised using descriptive statistics at each scheduled assessment time by actual treatment group.

Shift tables for laboratory values (excluding electrolytes) from baseline to worst value on-treatment categorized using the common toxicity criteria (CTC) grading based on local reference ranges will be produced. On-treatment is defined as data collected up until the last dose of olaparib/placebo. For parameters with no CTC grading, shift tables from baseline to worst value on-treatment will be provided using normal ranges for categorization. Shift tables for urinalysis values from baseline to worst grade on-treatment will also be provided.

Box-plots of absolute values for continuous laboratory assessments will be presented, with AZ project defined reference ranges indicated.

A scatter plot of alanine aminotransferase (ALT) versus total bilirubin, both expressed as multiples of the upper limit of normal (ULN), will be produced with reference lines at $3 \times \text{ULN}$

for ALT, and $2 \times \text{ULN}$ for total bilirubin. The scatter plot will be repeated for aspartate aminotransferase (AST) versus total bilirubin with reference lines at $3 \times \text{ULN}$ for AST, and $2 \times \text{ULN}$ for total bilirubin. In each plot, total bilirubin will be in the vertical axis.

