Appendix C: Study Schedule

Table 12 Study Schedule

Cycle/ Visit	Screen PART 1 (Patients with unknown BRCA status only)	Screen PART 2 (All patients)	Treatment Duration						Study treatment discontinued	30-Day follow- up	Survival Follow- up ^y	
			1 (28 days)			2	3+ (every 28 days)				Until DCO2	Between DCO2 & DCO3
Day		-28 to 0	1	8	15	22	29	57+			Every 8 weeks	Every 12 weeks
Visit window				±3d	±3d	±3d	±3d	±3d	±7d	±7d	±7d	±7d
Informed consent	X	X										
Randomisation f			X f									
Demographics	X	X										
Medical and surgical history, including blood transfusions a		X										
Prior cancer therapies including radiotherapy		X										
Inclusion/exclusion criteria	X (all * criteria) b	X										

Table 12 Study Schedule

	Screen PART 1 (Patients with unknown BRCA status only)	Screen PART 2 (All patients)	Treatment Duration						Study treatment discontinued	30-Day follow- up	Survival Follow- up ^v	
Cycle/ Visit			1 (28 days)			2	3+ (every 28 days)				Until DCO2	Between DCO2 & DCO3
Day		-28 to 0	1	8	15	22	29	57+			Every 8 weeks	Every 12 weeks
Visit window				±3d	±3d	±3d	±3d	±3d	±7d		±7d	±7d
Blood samples for gBRCA status c	X		X d									
Archival paraffin embedded tumour tissue or cytology sample e	X	X										
Concomitant medications		X	X	X	X	X	X	X	X	X	X	
CCI		■					■	■	■	■	■	
Vital signs		X g	X				X	X	X	X	X	
Physical examination h		X					X	X	X	X	X	
ECG i		X	As clinically indicated									

Table 12 Study Schedule

	Screen PART 1 (Patients with unknown BRCA status only)	Screen PART 2 (All patients)	Treatment Duration						Study treatment discontinued	30-Day follow- up	Survival Follow- up ^y	
Cycle/ Visit			1 (28 days)			2	3+			Until DCO2	Between DCO2 & DCO3	
Day		-28 to 0	1	8	15	22	29	57+		Every 8 weeks	Every 12 weeks	
Visit window			±3d	±3d	±3d	±3d	±3d		±7d	±7d	±7d	
Tumour assessment (modified RECIST) j		X (no more than 28 days before start of treatment) j	Every 8 weeks (± 1 week) until week 40 then every 12 weeks (±1 week), relative to the date of randomisation j							If patient does not have disease progression at the time of treatment discontinuation on tumour assessments should be continued per the CSP schedule k		
Haematology/clinical chemistry		X	X				X	X	X	X		

Table 12 Study Schedule

	Screen PART 1 (Patients with unknown BRCA status only)	Screen PART 2 (All patients)	Treatment Duration						Study treatment discontinued	30-Day follow- up	Survival Follow- up ^v	

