- k For patients who discontinue study treatment prior to disease progression, RECIST assessments will continue until objective disease progression (every 8 weeks (± 1 week) for the first 40 weeks, then every 12 weeks (± 1 week) relative to date of randomisation, until objective disease progression as defined by modified RECIST).
- l Haematology and clinical chemistry should be performed at screening and day 1 of every cycle. Safety blood samples do not need to be repeated on Day 1 of study treatment if assessed at least 3 weeks after the last dose of chemotherapy but within 7 days before starting study treatment, unless the investigator believes that it is likely to have changed significantly.
- m Coagulation test should be performed at screening and if clinically indicated.
- n Urinalysis should be performed at screening. After screening, urinalysis will only be required if clinically indicated.
- o In the event of suspected pregnancy during the study, the test should be repeated and, if positive, the patient discontinued from study treatment immediately.
- p Mandatory blood samples for biomarker analysis to be taken prior to dosing on Cycle 1 Day 1 and at disease progression.

- q CCI
- r Adverse events must be captured from time of consent. Only SAE's related to blood sampling for the Myriad gBRCA test will be collected at this visit.
- s Continuous Olaparib 300mg/ placebo twice daily dosing. Sufficient study treatment should be dispensed for at least each treatment period plus overage, however additional treatment can be dispensed to patients to last longer in accordance with local practice.
- t All anti-cancer treatments (including, but not limited to, chemotherapy and targeted agents), and the Investigator's opinion of response to them need to be recorded until end of study period (DCO3), plus the date of progression post discontinuation of study treatment, need to be recorded.
- u Second disease progression (PFS2) assessment will be performed by the Investigator and defined according to local standard clinical practice and may involve any of, objective radiological or symptomatic progression or death. Subsequent therapy will be collected for these patients from the time of treatment discontinuation until end of study period (DCO3).

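### Laboratory shift tables stop at the last dose, so later samples, including the scheduled 30-day one, cannot count towards the worst CTC grade, although AE summaries run 30 days further

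*SAP*

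**What the plan says.** SAP Section 4.2.13 (Laboratory assessments) plans "Shift tables for laboratory values (excluding electrolytes) from baseline to worst value on-treatment", graded by CTC on local reference ranges. Parameters without a CTC grade get normal-range shift tables, and urinalysis gets its own; both also use the worst on-treatment result. The period is closed by "On-treatment is defined as data collected up until the last dose of olaparib/placebo".

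Collection goes further. Section 3.4.4 states: "Laboratory data will be collected throughout the study, from screening to 30-day follow-up visit". In Appendix C, Table 12, the row "Haematology/clinical chemistry" is marked at screening Part 2, Day 1, Day 29, Day 57 and each later cycle, treatment discontinuation and the 30-day follow-up. It is not marked on Days 8, 15 or 22. The footnote agrees: "Haematology and clinical chemistry should be performed at screening and day 1 of every cycle". Section 3.4.9 adds "Any assessments made on day 1 will be considered pre-dose", so the Day 1 sample can serve only as baseline.

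For adverse events, Section 4.2.13 uses a longer period: "The summary tables will include all AEs that occurred after the start of treatment up until the end of the 30 day follow-up period". The AE event rate counts time at risk to "MINIMUM([date of last dose + 30-day safety follow-up period], OS date, DCO"). Section 3.4.9 likewise treats concomitant medication as on-treatment up to and including 30 days after the last dose. The SAP gives no reason for a shorter laboratory period.

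**The concern.** Safety and tolerability, with haematology and clinical chemistry findings named, is a stated objective (Section 1.1). The shift table is the only laboratory output described in the SAP that tabulates worst CTC grade by treatment group. Samples collected by design after the last dose are left out of it.

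The omission works in one direction. A maximum over a shorter period cannot exceed the maximum over a longer period that contains it, so the rule can lower a patient's worst grade but never raise it. It matters most where values are still worsening when dosing ends: a patient who stops between 4-weekly samples, or one whose drug is interrupted and never restarted. In the second case the last dose precedes the interruption, and every sample taken during it falls outside the period. The SAP expects some patients to end this way: the dose-intensity example in Section 3.4.3 includes a patient who progresses during an interruption.

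The two windows can also produce a report that disagrees with itself. A grade 3 anaemia first seen a week after the last dose and reported as an AE would appear in the AE tables but not in the haematology shift table.

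**Working it through.** The SAP states no figure on this point to reproduce. The check compares the windows and applies date arithmetic to the schedule.

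**Windows side by side (SAP)**

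| Output | End of period | Section |
|---|---|---|
| Laboratory shift tables | Last dose | 4.2.13 |
| AE summary tables | End of 30-day follow-up | 4.2.13 |
| AE time at risk | Last dose + 30 days, capped at OS date and data cut-off | 4.2.13 |
| Concomitant medication | Last dose + 30 days | 3.4.9 |
| Laboratory collection | 30-day follow-up visit | 3.4.4, Appendix C |

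**Inputs.** Scheduled post-baseline cycle samples fall on s = 29, 57, 85, … (every 28 days). Let t be the study day of the last dose. A sample counts if s ≤ t. Visit windows and unscheduled samples are set aside at first.

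**Step 1: last counted cycle sample.** Gap g(t) = t − max{s : s ≤ t}.

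| Last dose (t) | Last counted sample | Gap (days) | Nominal 30-day sample |
|---|---|---|---|
| 20 | none | – | Day 50 |
| 28 | none | – | Day 58 |
| 29 | 29 | 0 | Day 59 |
| 40 | 29 | 11 | Day 70 |
| 56 | 29 | 27 | Day 86 |
| 70 | 57 | 13 | Day 100 |

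From Day 29 on, the gap is 0 to 27 days. If last doses were spread evenly over the cycle (an assumption), the mean gap is (0 + 1 + … + 27)/28 = 378/28 = 13.5 days.

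**Step 2: early stops.** With a last dose on Days 1 to 28, no nominal cycle sample counts after baseline. The ±3-day visit window softens this: the Day 29 sample may be drawn on Day 29 − 3 = 26, so a last dose on Days 26 to 28 can still have one.

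**Step 3: the two end-of-treatment samples.** The 30-day sample is always after the last dose, so it never counts. The discontinuation sample counts if taken before the last dose and is excluded if taken after it. A same-day sample is unclear, because the definition does not say whether the day of the last dose is included.

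**Step 4: a plain 30-day extension.** The 30-day visit appears to carry a ±7-day window in Table 12, so its sample may be drawn as late as day 30 + 7 = 37 after the last dose. A cut at exactly 30 days would lose samples from days 31 to 37.

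These gaps describe when sampling occurs. They do not measure how many grades change, and the SAP has no input from which that could be calculated.

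**The case against.** The case for leaving the rule alone has several sound parts.

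- **The result that triggers a stop is usually kept.** If a blood result prompts a hold or a stop, it was normally drawn while the patient was still dosing, so it counts. Only later worsening is lost. Unscheduled samples up to the last dose also count: Section 3.4.9 gives them the potential to enter summaries. This stands, and it limits the reach of the point.
- **Later values are reported elsewhere.** The discontinuation and 30-day visits keep their own place in the by-visit summaries. By-patient listings show CTC grade. The liver plots and tabulations state no last-dose limit. Reported abnormalities are graded in the AE tables. This stands too, but by-visit statistics and listings do not give worst grade by arm, the liver outputs do not cover haematology, and AE tables depend on the investigator reporting the abnormality.
- **A last-dose cut-off isolates study drug.** Treatment normally runs to progression, and Section 1.2 anticipates re-treatment with the earlier platinum regimen. Post-dose values may therefore reflect the disease or new chemotherapy, and a shift table carries no causality assessment. This is the strongest objection. Ending the window at subsequent anti-cancer therapy, with the last-dose table kept alongside, answers the chemotherapy part. Some influence of progression remains.

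A reader might infer that every patient who stops loses two scheduled samples, or that everyone who stops for toxicity has an understated grade. Neither follows: a discontinuation sample taken before the last dose counts, and a grade changes only if the worst value comes after the last dose and nothing earlier matched it.

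**Conclusion.** The point holds as a defect in a descriptive safety output. Followed as written, the rule removes the 30-day sample from every worst-grade shift table, together with any discontinuation or dose-hold sample taken after the last dose. It conflicts without explanation with the 30-day windows used for AEs and concomitant medication. Worst grade may be understated in some patients, and the rule can never overstate it relative to the longer window.

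The size in patients is unknown. The 0 to 27 day gap assumes nominal visit days and scheduled cycle samples only; the 13.5-day mean also assumes evenly spread stopping days. A reader might go on to infer that the contrast between arms is biased in olaparib's favour. The SAP gives no rate of stopping for toxicity by arm and no post-dose laboratory data, so neither the direction nor the size of an arm difference can be established. No efficacy analysis is affected.

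**What to change.** In Section 4.2.13, define the window for the laboratory worst-value shift tables as after the first dose up to the earliest of:

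- last dose + 30 days, with the 30-day follow-up sample admitted if taken within its visit window;
- the start of subsequent anti-cancer therapy;
- data cut-off.

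State that a sample taken on the day of the last dose counts. Keep the last-dose shift table as a second display, so that readers can see what the follow-up samples add.

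The cost is a few lines of SAP text, a date condition in the programs and one more set of tables. The samples are already scheduled, and the start of subsequent therapy is already needed for TFST (Section 3.2.4). The remaining downside is that some added values may reflect progression rather than study drug, which the paired display makes visible. The vital-sign shift table need not change for this point.

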4.2 Analysis Methods

A single interim PFS analysis for futility will be performed when 50% of the final number of progression events has been reached (approximately 44 PFS events). A final PFS analysis will be performed when approximately 87 progression events have occurred (60% maturity) (DCO1). No further analyses of PFS are planned beyond this point.

One interim analysis for OS will be performed at the time of the final PFS analysis (approximately 87 PFS events). A final formal analysis of OS will be performed when approximate 106 death events have occurred (DCO2). **CCI**

Individual efficacy response data will be listed in a by-patient listing.

A summary of the outcome variables to be analysed at each DCO is shown in [Table 10](#) below.

Table 10 **Timing of Statistical Analyses**

Timing of analysis	Outcome Variable
Interim PFS when ~44 PFS events reported	PFS
Final PFS when ~87 PFS events reported (DCO1)	PFS, PFS2, TDT, TFST, TSST, OS, ORR, BoR, DoR and adjusted mean change from baseline in global HRQoL score.
Final formal OS when ~106 OS events reported (DCO2)	OS, PFS (investigator assessment), PFS2, TDT, TFST, TSST, and adjusted mean change from baseline in global HRQoL score.
CCI	

Safety variables will be analysed at each analysis time point.

There will be no further analyses done unless requested by health authorities.

The treatment comparison is olaparib 300 mg bid versus placebo.

The following table details which efficacy endpoints are to be subject to formal statistical analysis, together with pre-planned sensitivity analyses making clear which analysis is regarded as primary for that endpoint.

Table 11 **Formal Statistical Analyses to be Conducted and Pre-Planned Sensitivity Analyses**

Endpoints Analysed	Notes
PFS	Primary analysis: log-rank test using BICR data
	Key sensitivity analyses: log-rank test using BICR data in randomised patients confirmed as gBRCA mutation positive by the Myriad test (if subset of FAS)
	Additional sensitivity analyses:
	1) Evaluation time bias analysis; log-rank test using BICR data
	2) Attrition bias analysis (using alternative censoring rules); log-rank test using BICR data
	3) Ascertainment bias analysis; log-rank test using investigator data

Table 11 Formal Statistical Analyses to be Conducted and Pre-Planned Sensitivity Analyses

Endpoints Analysed	Notes
	4) Deviation bias analysis (if meaningful to do); log-rank test using BICR data
OS	Primary analysis: log-rank test

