DCO1 took place on 15th Jan 2019 at which time details of the alpha spending plan were updated. Based on the observed 71 OS events at the interim analysis, i.e. 67% of the 106 OS

events which are planned for the final analysis, statistical significance for OS was to be declared if the null hypothesis for progression-free survival (PFS) was rejected and the observed one-sided p-value for OS was $p < 0.006$. Also, given that the number of OS events at the final analysis is planned as 106 the one-sided significance level to be applied for the final analysis will be $p < 0.023$.

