Liver biochemistry test results over time for patients who show elevated ALT or aspartate aminotransferase (AST) ($\geq 3 \times \text{ULN}$) and elevated total bilirubin ($\geq 2 \times \text{ULN}$) (elevated results do not need to be present at the same visit), or a total bilirubin of $\geq 5 \times \text{ULN}$ will be tabulated and plotted.

All laboratory summaries and listings will be presented by actual treatment group.

By-patient listings of laboratory assessments will be provided showing at least: laboratory parameters, actual time point, measurements/results, CTC grade (if available), and the change from baseline value (for continuous data) (if appropriate). In addition, a flag will indicate if the value was out of normal range, if appropriate:

- Laboratory reference ranges
- Haematology
- Serum chemistry
- Urinalysis
- Individual patient data with elevated ALT or AST plus total bilirubin
- Pregnancy report data

Electrocardiograms

If available, overall evaluation of ECG will be summarised by visit as normal, abnormal or borderline.

All ECG data will be listed by actual treatment group.

Vital signs

Vital signs (systolic blood pressure [SBP], diastolic blood pressure [DBP], pulse rate, body temperature and weight) will be summarised by time point in terms of absolute values, changes from baseline and percentage changes from baseline at each scheduled measurement by actual treatment group. A shift table comparing baseline to maximum value on treatment will be summarised for SBP, DBP and pulse rate by actual treatment group, using the following normal ranges: SBP = 100 - 160 mmHg; DBP = 60 - 95 mmHg; pulse rate = 55 - 95 bpm.

Box plots for absolute values in SBP, DBP, pulse rate, body temperature, and weight will be presented.

Vital signs data will be listed.

Other

- Any concomitant procedures patients experiencing during the study will be listed in a by-patient listing
- Patients experiencing a Hy's Law incident will be tabulated and details will be included in by-patient listings. Hy's Law incidents are those cases where a patient shows an AST or ALT $\geq 3 \times \text{ULN}$ or total bilirubin $\geq 2 \times \text{ULN}$. Please refer to Appendix D of the CSP for further instructions.

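### The Hy's Law definition joins the transaminase and bilirubin cut-offs with *or*, so isolated elevations would be reported as Hy's Law incidents

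*SAP*

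**What the plan says.** The last bullet of SAP section 4.2.13 (Other) sets up a Hy's Law output: "Patients experiencing a Hy's Law incident will be tabulated and details will be included in by-patient listings". It then defines the term: "Hy's Law incidents are those cases where a patient shows an AST or ALT $\geq 3 \times \text{ULN}$ or total bilirubin $\geq 2 \times \text{ULN". It closes with a pointer to the protocol: "Please refer to Appendix D of the CSP for further instructions".

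Earlier in section 4.2.13, under Laboratory assessments, liver test results over time are to be shown for patients with "elevated ALT or aspartate aminotransferase (AST) ($\geq 3 \times \text{ULN}$) and elevated total bilirubin ($\geq 2 \times \text{ULN". The SAP adds there that the two elevations may fall at different visits. A second route into that output is "or a total bilirubin of $\geq 5 \times \text{ULN}$ will be tabulated and plotted". The matching by-patient listing is for raised ALT or AST plus total bilirubin. The scatter plots of each transaminase against bilirubin draw their reference lines at 3×ULN and 2×ULN.

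On the use of these outputs, section 4.2.13 states: "No formal statistical analyses will be performed on the safety data". Section 4.2 states: "Safety variables will be analysed at each analysis time point".

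**The concern.** The two rules use the same thresholds but opposite connectors. The bullet needs either elevation. The liver output needs both, unless bilirubin alone reaches 5×ULN. Because the bullet is a complete definition and the only one in the SAP, a programmer following it would code *or*.

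Isolated elevations would then appear, by treatment group, under a Hy's Law heading. Some of those patients would be missing from the detailed liver tabulation and plot, so a reader could not reconcile the two outputs.

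Consistency over time is also in question. Safety is reported at each cut-off, and section 4.2.1 records that "DCO1 took place on 15th Jan 2019", about a year before this SAP version (31 January 2020). If the table at DCO1 was built on a different rule from the one applied later, the counts are not comparable.

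**Working it through.** The SAP states no figure for this output, so there is nothing to reproduce. The check compares the two rules as sets.

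**Inputs (SAP section 4.2.13)**
- A: AST or ALT ≥3×ULN
- B: total bilirubin ≥2×ULN
- C: total bilirubin ≥5×ULN, which lies inside B

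**Rules**
- Hy's Law bullet: A or B
- Liver biochemistry output: (A and B) or C
- Paired criterion alone: A and B

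| Patient's pattern | Hy's Law bullet | Liver output | Paired criterion |
|---|---|---|---|
| A and B | in | in | in |
| A only | in | out | out |
| B only, bilirubin 2 to <5×ULN | in | out | out |
| B only, bilirubin ≥5×ULN | in | in | out |
| Neither | out | out | out |

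**Excess counts**
- Bullet count = n(A only) + n(B only) + n(A and B).
- Excess over the paired criterion = n(A only) + n(B only) ≥ 0.
- Excess over the liver output = n(A only) + n(B only with bilirubin <5×ULN) ≥ 0. This is the same or smaller, because an isolated bilirubin ≥5×ULN is in both outputs.

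Every patient in the liver output is also in the Hy's Law table, so the *or* rule can add patients but cannot lose a paired case. The SAP gives no rates of liver test elevation, so the excess cannot be sized.

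**Scale per patient**
- Section 1.3 plans about 145 patients at 3:2: 145 × 3/5 = 87 on olaparib and 145 × 2/5 = 58 on placebo. This 87 is an arm size, not the 87 PFS events that trigger the final PFS analysis.
- Assumption: all patients are dosed as randomised.
- One isolated elevation adds 1/87 = 1.15 percentage points on olaparib or 1/58 = 1.72 percentage points on placebo.

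**The case against.** The strongest reply is that these are two differently named outputs, which may use different selection rules. The liver sentence is not labelled Hy's Law. That part stands: reading the paired rule into the bullet is an inference. It rests on the identical cut-offs, on the listing that combines a transaminase with bilirubin, and on the scatter plots drawn at the same lines.

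A second reply is that Appendix D of the protocol may settle the definition. It is not at hand, so this cannot be tested. But the bullet cites it for further instructions after giving a full definition of its own. If the appendix uses the paired rule, the SAP conflicts with it. If it uses *or*, the mismatch within section 4.2.13 remains.

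A third reply is that little harm follows. Paired cases are already tabulated, plotted and listed, and none is lost under *or*. This is true, and it keeps the point minor. It does not justify the Hy's Law label on isolated elevations.

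Finally, nothing shows that a different rule was used at DCO1. The visible amendment entries record no change to this definition, although some are redacted. The DCO1 step is therefore only a conditional check.

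**Conclusion.** The concern holds. As written, the SAP's Hy's Law definition admits patients with a single elevation, at odds with the paired criterion that the same section applies to the same cut-offs. The Hy's Law count is inflated by n(A only) + n(B only) relative to the paired criterion. That excess is zero or positive and of unknown size. Each such patient is worth about 1.1 percentage points on olaparib or 1.7 on placebo, if the planned numbers are randomised and all are dosed as randomised.

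The severity is minor. The effect is confined to descriptive safety tables and listings, and no efficacy result, significance level or interim decision uses the flag. The presence of *or* is certain. The intended *and* is inferred and depends on Appendix D of the protocol.

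**What to change.** Reconcile the Hy's Law bullet with the liver biochemistry criterion in section 4.2.13 and with Appendix D of the protocol. Subject to that check, define the flag for the table and listings as (AST or ALT ≥3×ULN) **and** total bilirubin ≥2×ULN. State explicitly whether the two elevations may fall at different visits. The liver output allows this, and the same rule should carry over so that the flag can be programmed without ambiguity.

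Then check which rule the DCO1 table used. If it was *or*, footnote or rerun that table so that the cut-offs can be compared.

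The cost is one connector and a timing clause in the SAP, a small change to one derived flag, and a check of one table with a possible footnote or rerun. No new data are needed.
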